The N-CRM method assumes that the probability of experiencing a DLT is related to dose according to a logistic regression model. The model actively seeks a dose level that produces a pre-specified probability of a DLT occurring by using safety data from all

enrolled subjects to compute a more precise dose-toxicity curve. The model is carried out using Bayesian methods, which requires an initial estimation of prior distribution which characterizes the shape of the dose-toxicity curve. In this case, a weakly informative prior was selected based on clinical experience reported to date for anti-HER3 mAbs (which have not been associated with reported DLTs) and the nonclinical safety data for GSK2849330.

As the study progresses, the absence or presence of DLTs in subjects enrolled at each dose level provides additional information for the model and results in an adjustment of the estimation of distribution to characterize the shape of the dose-toxicity curve (also called posterior distribution). The posterior distribution is then evaluated to identify the dose closest to the acceptable toxicity interval, which is pre-specified as the interval from 16% - 33% DLT rate. This range was selected as the equivalent of between a 1 out of 6 and 1 out of 3 (or 2 out of 6) toxicity rate which guides the traditional 3+3 dose escalation decision.

Implementation of N-CRM: The N-CRM model implementation will be performed using Fixed and Adaptive Clinical Trial Simulator (FACTS) (Version 2.3 or higher) from Tessella.

Bayesian Prior

The N-CRM methodology requires that a Bayesian prior for the toxicity curve be pre-specified. The Bayesian prior used for this design was determined using the quantile method. For each dose, an estimate of the median probability of DLT was specified, along with a 95% credible interval. The 95% credible intervals are intentionally wide due to limited information about the toxicity profile of GSK2849330 in humans. [Table 1](#) shows the median prior probability of experiencing a DLT at the given cumulative dose along with a 95% credible interval around the median:

Table 1 Table of Specified Prior Probability of DLT (with 95% Credible Interval)

Anticipated Dose (mg/kg)	2.5% Quantile for Probability of DLT	Median for Probability of DLT	97.5% Quantile for Probability of DLT
1.4	0.0009739	0.00415	0.5
3	0.002085	0.00851	0.6
10	0.006915	0.02891	0.7
30	0.02046	0.08198	0.8

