The 2.5% quantile and median of the prior distribution are based on Roche RGA7116 study human safety data [[Meulendijks, 2013](#)] conservatively treating AEs that resulted in discontinuation as if they were DLTs. The 97.5% quantile of the prior distribution is increased by empirical adjustment to weaken the prior by inflation of variance.

Dose recommendation: Dose recommendation output from the N-CRM model will be based on the posterior probabilities that the DLT rate for each escalation dose lies in one of the following categories:

- [0%,16%) range of minimal toxicity
- [16%, 33%) range of acceptable toxicity
- [33%, 60%) range of excessive toxicity
- [60%, 100%) range of unacceptable toxicity

After each cohort, a recommendation will be made to either: 1) escalate to the next dose or regimen, 2) de-escalate, 3) recruit more subjects at the current dose, or 4) stop. The recommended dose will be the one with the highest probability of having a DLT rate in the acceptable toxicity range [16%, 33%), subject to the constraint that no dose may be skipped during dose escalation. The recommended dose has an additional requirement that the sum of the posterior probabilities of the DLT rate lying in the excessive toxicity or unacceptable toxicity range must be less than 25%. Additional subjects may also be enrolled at any specified dose level to further characterize the safety, as with traditional dose-escalation methods.

Prior to dose escalation/de-escalation, a meeting will be convened to discuss available safety, and the recommendation from the N-CRM model. The data will be reviewed by the investigator(s) and GSK study team which may include the Medical Monitor, statistician, and pharmacokineticist. The dose escalation rationale and decision for the subsequent cohort will be documented in writing with copies maintained at each site and in the GSK study files.

The initial dose levels to be evaluated are outlined in Section [3.6.3](#).

Additional subjects may also be enrolled at any specified dose level to further characterize safety. Additional doses and schedules and loading doses may be explored, following the rules outlined for dose escalation, based on emerging safety, PK, and PD data.

PK/PD cohort(s): Once a given dose escalation cohort is filled, additional subjects may be enrolled into a PK/PD cohort (at any dose level determined to be tolerable) to allow for the collection of data on the PD effects of GSK2849330 as well as additional PK data.

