3.3.2. Maximum Tolerated Dose

In the context of the N-CRM approach as described in Section 3.3, the MTD is defined as the dose with the highest posterior probability of subjects experiencing a DLT, in the first 28 days on treatment in the target interval [16%, 33%]. These probabilities 16% and 33% were chosen to be consistent with the traditional 3+3 design toxicity boundary which is 1/6 and 1/3.

Additional dosing schedules with lower dose intensity may be explored as long as they do not exceed the MTD.

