The proposed starting dose is 1.4 mg/kg, administered once-weekly. According to ICHS9 guidance, calculating a starting dose based on HNSTD/6 in the most relevant species (cynomolgous monkey) yields a starting dose of \sim 16 mg/kg/wk. We selected a more conservative starting dose of 1.4 mg/kg/wk, slightly above the MABEL calculated from tumor xenograft studies, which in turn suggests that clinical activity may be observed at dose levels of 1.2 mg/kg and higher.

Table 3 Dose Levels

Cohort	Dose	N Dose Escalation Cohorts	N PK-PD Cohorts
1	1.4 mg/kg weekly	1 (minimum)	up to 3
2	3 mg/kg every 2 weeks	3 (minimum)	up to 3
3	10 mg/kg every 2 weeks	3 (minimum)	up to 3
4	30 mg/kg every 2 weeks	3 (minimum)	up to 3
5	30 mg/kg weekly (optional change to every 2 weeks after 24 weeks of treatment)	3 (minimum)	up to 3
Additional optional cohorts may be enrolled at different dose levels and intensities			

Maximum Proposed Dose

The maximum proposed dose of 30 mg/kg for weekly, bi-weekly or every three week dosing was selected based on PK-PD extrapolations which predict target engagement > 90% and tumor saturation should be achieved at or below this dose, and based on practical considerations (e.g., drug product supply and production capacity) Emerging PK, safety and tolerability data may cause the proposed maximum dose to be adjusted downward (see Section 3.3 for details of the N-CRM model assessment of safety data).

Dose Escalation

The proposed dose escalation scheme is based on a half-log step size, with the exception of the 30 mg/kg/wk dose and the nominal doses shown in Table 3 represent the maximum dose which may be selected. The study team, in discussion with the investigator(s), may select other doses or alternative schedules besides those shown, based on emerging safety, tolerability, PK and/or PD data.

Dosing Interval

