13.2. Sample Size Determination

13.2.1. Part 1: Dose-Escalation Phase

The total number of subjects in the Part 1 dose escalation will depend on the number of dose escalations needed, but the minimum number of subjects anticipated to complete dose escalation is 13 and the anticipated number of subjects is approximately 34 subjects. The selection of sample size 34 is based on the goal of fully exploring available dose ranges for purposes of selecting an appropriate regimen(s) for Part 2. This will include a number of cohorts to establish an initial understanding of the dose-response relationship as well as to evaluate a range of PD biomarkers that may reveal the biological activity of GSK2849330. The initial cohort (1.4 mg/kg) will have 1 subject and Cohorts 2 through 5 will have 3 subjects in the dose escalation phase and up to an additional 3 subjects with

evaluable pre- and on-treatment paired biopsies in each of these cohorts for the PK/PD cohorts. See Section 3.3 and Table 3 for additional details. The actual number of cohorts and subjects will depend in part on the observed toxicity and the PK and PD observed during the dose escalation.

Simulations were conducted to determine the average sample size and percentage of time each dose was selected under 3 different scenarios: almost no toxicity scenario, little toxicity scenario and moderate toxicity scenario. For each scenario, 5000 clinical trials were simulated using the planned doses. Details are provided in Table 14.

The specified prior probabilities discussed in Section 3.3 were used to determine an explicit equation for the prior distribution using the FACTS software. The parameters (s.d.) of the explicit distribution are $\alpha=-5.334(1.9913)$, $\ln(\beta)=-0.0579(0.1018)$, and $\rho=-0.9977$ where α and $\ln(\beta)$ are distributed as bivariate normal with correlation ρ .

Table 14 Simulation Results for Various Scenarios

Dose (mg/kg)	Scenario 1: Almost No Toxicity		Scenario 2: Little Toxicity		Scenario 3: Moderate Toxicity	
	True DLT Rate	Percent of Trials Selecting Dose as MTD (%)	True DLT Rate	Percent of Trials Selecting Dose as MTD (%)	True DLT Rate	Percent of Trials Selecting Dose as MTD (%)
1.4	0.00005	0	0.0005	0.8	0.05	5.2
3	0.0005	0	0.1	10	0.1	14.2
10	0.005	0.2	0.2	33	0.2	37.4
30	0.055	99.8	0.25	56.2	0.3	43.2

The average sample size over the 5000 clinical trials simulated under Scenarios 1-3 was 15.2, 15.5, and 15.1 respectively.

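### The N-CRM prior is described at cumulative dose but built on per-infusion dose, and with no schedule term the overdose rule cannot distinguish 30 mg/kg weekly from 30 mg/kg every 2 weeks

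*Protocol*

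**What the plan says.** Protocol 3.3 (Bayesian Prior) introduces Table 1 as a table that "shows the median prior probability of experiencing a DLT at the given cumulative dose along with a 95% credible interval around the median". Its dose column lists 1.4, 3, 10 and 30 mg/kg, the nominal infusion doses. The period over which dose would accumulate is not given, and the word *cumulative* is not used again for the model.

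The model statement is: "The N-CRM method assumes that the probability of experiencing a DLT is related to dose according to a logistic regression model". No regimen or schedule term is mentioned. Section 13.2.1 gives the fitted prior for α and ln(β), and Table 14 simulates the same four doses. SAP 4.1 and 5.1 follow the same pattern.

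Table 3 (3.6.3) mixes schedules: Cohorts 1 and 5 are weekly, while Cohorts 2 to 4 are every 2 weeks (Cohort 2 is "3 mg/kg every 2 weeks"). Section 3.3 expects the model to recommend a next dose or regimen, subject to an overdose rule: "the sum of the posterior probabilities of the DLT rate lying in the excessive toxicity or unacceptable toxicity range must be less than 25" per cent.

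**The concern.** The dose covariate decides how a DLT in one cohort carries over to another regimen, and so the overdose probability. If every cohort had the same schedule, per-infusion and cumulative dose would differ only by a constant and the wording would hardly matter. Here the schedule changes twice, after Cohort 1 and again at Cohort 5.

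The second change matters more. From Cohort 4 to Cohort 5 the infusion dose stays at 30 mg/kg and the 28-day total doubles. A per-infusion model sees no step there; a cumulative model sees a twofold step. The documents say one thing and tabulate the other, so a reader cannot tell what the overdose rule would return for 30 mg/kg weekly, or reproduce it.

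**Working it through.** **Inputs.** Table 1 medians: 0.00415, 0.00851, 0.02891, 0.08198. Table 3 regimens. The 28-day DLT window of 3.3.1. The 13.2.1 prior: α = -5.334 (SD 1.9913), ln β = -0.0579 (SD 0.1018), correlation -0.9977. Overdose limit: P(DLT rate ≥ 33%) below 25%.

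**28-day totals.** 4 × 1.4 = 5.6; 2 × 3 = 6; 2 × 10 = 20; 2 × 30 = 60; 4 × 30 = 120 mg/kg. No Table 1 row equals any of these.

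**Which scale produced Table 1?** Median odds divided by infusion dose, p/(1-p)/d, are 0.00298, 0.00286, 0.00298 and 0.00298. Holding the odds per mg/kg at the first row's value predicts:

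| Row (mg/kg) | Table 1 | per infusion | 28-day cumulative |
|---|---|---|---|
| 1.4 | 0.00415 | 0.00415 | 0.00415 |
| 3 | 0.00851 | 0.00885 | 0.00445 |
| 10 | 0.02891 | 0.02891 | 0.01466 |
| 30 | 0.08198 | 0.08198 | 0.04274 |

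The per-infusion rule reproduces three rows exactly and the 3 mg/kg row within 4%. The cumulative rule gives about half the stated values from 3 mg/kg up. Table 1 was therefore built per infusion.

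**Reproducing the prior.** I assume logit p = α + β ln(d/d_ref); the documents do not state d_ref. With d_ref = 1.4 mg/kg on the per-infusion scale, the 13.2.1 prior gives medians 0.0048, 0.0098, 0.0300 and 0.0801, close to Table 1. Its 97.5% quantiles (0.19 to 0.72) fall short of the specified 0.5 to 0.8.

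**Overdose probability for 30 mg/kg weekly.** Prior draws (400,000 to 1,000,000) are weighted by the binomial likelihood of 0/1, 0/3 and 0/3 DLTs in Cohorts 1 to 3 (0/7 in all) and the count shown in Cohort 4. Doses entered are 1.4, 3, 10, 30, 30 per infusion, or 5.6, 6, 20, 60, 120 cumulatively.

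| DLTs at 30 mg/kg every 2 weeks | per infusion, d_ref 1 / 1.4 | cumulative, d_ref 1 / 1.4 | cumulative, d_ref 2.8 |
|---|---|---|---|
| 0/3 | 0.016 / 0.011 | 0.119 / 0.090 | 0.050 |
| 1/6 | 0.041 / 0.034 | 0.249 / 0.210 | 0.149 |
| 1/3 | 0.121 / 0.103 | 0.419 / 0.368 | 0.280 |
| 2/6 | 0.169 / 0.151 | 0.545 / 0.500 | 0.420 |
| 2/3 | 0.378 / 0.347 | 0.745 / 0.706 | 0.629 |

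The rescaled reference 2.8 (2 × 1.4) leaves the every-2-week cohorts where the per-infusion scale puts them. Reference 5.6 (4 × 1.4) does the same for Cohort 1 and gives 0.207 after 1/3 and 0.346 after 2/6.

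Taking d_ref from 1 to 1.6 on both scales, the 2/6 case is 0.14-0.17 against 0.48-0.55, and 0.35-0.42 with the cumulative axis rescaled to 2.8-5.6. The 1/3 case is 0.10-0.12 against 0.35-0.42, and 0.21-0.28 rescaled.

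**Sensitivity.** With a prior refitted to Table 1 in place of the 13.2.1 parameters, 2/6 still splits (0.100 against 0.281-0.356). 1/3 splits only if the cumulative axis is not rescaled (0.062 against 0.260, or 0.170 rescaled).

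Table 14 could not be reproduced, because its stopping rule and maximum sample size are not stated; it does not help to separate the scales.

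**The case against.** The strongest reply is that *cumulative* is one stray word. Table 1, the simulations and both SAP sections work with per-infusion doses, and nothing suggests that trial data would be entered in FACTS on a different scale from the prior. That stands: a prior-data mismatch is not shown. But deleting the word does not supply a way for schedule to enter the model, and that gap is what leaves the weekly cohort unassessed.

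A second reply is that the model only guides escalation and the team also reviews safety, PK and PD data. That lowers the consequence. It does not make the stated overdose rule informative for the weekly regimen.

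A third is that the cumulative results depend on an unstated reference dose. This is right, and it removes the 1/3 split at reference 5.6. It does not remove the 2/6 split.

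Three stronger readings are tempting and not supported:

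- *A DLT in the first subject would reverse the decision.* With references of 1-1.6, staying at 1.4 mg/kg weekly gives 0.19-0.23 per infusion against 0.31-0.36 cumulatively. On the cumulative axis, references of 4 and 5.6 bring this to 0.228 and 0.202, with no split. Escalation to 3 mg/kg every 2 weeks is barred either way (0.357 against 0.370 at reference 1). Section 3.6.3 already reports PK through 10 mg/kg, so that decision is past.
- *The readings always conflict.* On the planned no-DLT path both allow every step.
- *Section 3.3.2 adds a third scale.* Its sentence, "Additional dosing schedules with lower dose intensity may be explored as long as they do not exceed the MTD", refers to dose intensity, which over a fixed 28 days ranks regimens as cumulative dose does. It is not presented as a model covariate.

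**Conclusion.** The concern holds in limited form. The introducing sentence contradicts Table 1, and the model as described has no means of telling 30 mg/kg weekly from 30 mg/kg every 2 weeks at twice the 28-day dose.

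The choice of scale can reverse the overdose result for the weekly regimen when DLTs have occurred at 30 mg/kg every 2 weeks. The reversal after 2/6 held at every reference dose tried; after 1/3 it depends on the reference dose. After 0/3 or 2/3 both readings decide alike, and so do they after 1/6, though at reference 1 the cumulative value (0.249) is practically at the limit.

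These sizes rest on the assumed logistic form in log dose, the assumed reference doses, accumulation over the 28-day DLT window, and no DLTs in Cohorts 1 to 3.

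**What to change.** Reconcile the passages on one dose metric throughout Protocol 3.3, Table 1, 13.2.1 with Table 14, and SAP 4.1 and 5.1, and state its time window and reference dose. There are two ways to do it:

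1. Put prior and data on a 28-day cumulative scale. Rebuild Table 1, add an entry for 30 mg/kg weekly, and re-run the FACTS simulations.
2. Delete *cumulative*, keep the per-infusion scale, and add a stated way for schedule to enter the model, so that 30 mg/kg weekly has its own DLT probability.

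The cost is wording in both documents plus a FACTS re-run: certainly for the first option, and for the second if the added schedule handling changes the model. Neither requires a change to any dose level.

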3.3.1. Dose-Limiting Toxicity

An event will be considered a DLT if it occurs within the first 4 weeks (28 days) of treatment, and meets one of the following criteria unless it can be clearly established that the event is unrelated to treatment:

- a. Grade 3 or greater non-hematologic toxicity as described in Common National Cancer Institute-Terminology Criteria for Adverse Events (NCI-CTCAE) version 4.0 [NCI, 2009] that cannot be controlled with routine supportive measures (e.g., antiemetics, antidiarrheals, antihistamines).
- b. Grade 4 neutropenia lasting >5 days.
- c. Febrile neutropenia, of any grade or duration as defined by NCI-CTCAE version 4.0 [NCI, 2009].
- d. Grade 4 thrombocytopenia, or Grade 3 thrombocytopenia associated with bleeding.
- e. Alanine aminotransferase (ALT) >3x upper limit of normal (ULN) with bilirubin >2x ULN.
- f. Any Grade 2 or greater NCI-CTACAE version 4.0 [NCI, 2009] toxicity that in the judgment of the investigator and GSK Medical Monitor, would be considered dose-limiting.
- g. Grade 3 or greater decrease in left ventricular ejection fraction (LVEF).

3.3.2. Maximum Tolerated Dose

In the context of the N-CRM approach as described in Section 3.3, the MTD is defined as the dose with the highest posterior probability of subjects experiencing a DLT, in the first 28 days on treatment in the target interval [16%, 33%]. These probabilities 16% and 33% were chosen to be consistent with the traditional 3+3 design toxicity boundary which is 1/6 and 1/3.

Additional dosing schedules with lower dose intensity may be explored as long as they do not exceed the MTD.

3.4. Part 2: Molecularly-Defined Tumor Histology Groups

Part 2 can begin once the recommended dose and schedule is identified in Part 1. It is possible that more than one dose and/or schedule will be evaluated in Part 2 if available PK, PD and safety data suggest that multiple doses and schedules have desirable biologic activity or if an MTD cannot be established.

The selected dose level(s) will be evaluated in Part 2 for confirmation of safety and tolerability, as well as preliminary assessment of clinical benefit, in at least 4 molecularly-defined tumor histology groups of subjects with HER3 or HER3 and NRG1 expressing tumors. Group 1 will include subjects with HER3- expressing melanoma. Group 2 will include subjects with HER3-expressing gastric cancer. Group 3 will include subjects with HER3 expressing and NRG1-expressing cancers of the head and neck. Group 4 will include subjects with HER3 expressing and NRG1-expressing NSCLC. All subjects must have archival tissue available for HER3 and if required NRG1 testing or be willing to undergo a tumor biopsy using a procedure that is safe for the subject, to provide a sample for testing.

Each group will initially enroll 12 subjects with the option of expanding to a maximum of 30 subjects if futility criteria are not met using well established methodology of [Lee, 2008] (See Section 13.2.2 and Section 13.6.2 for additional details).

Subjects will be required to have disease amenable to biopsy and agree to pre-and on-treatment tumor biopsies, using a procedure that is safe for the subject. Pre-and on-treatment biopsies are mandatory for all subjects in all groups. GSK will closely monitor and evaluate the collection of evaluable biopsies and will notify the participating centers of any change to the collection requirements for any or all groups.

3.5. Intra-subject Dose-Escalation

A subject's dose level may be increased up to the highest dose level that has previously been confirmed by the investigator and GSK medical monitor as not exceeding the MTD. Intra-subject dose escalations will be allowed in both Part 1 and Part 2 (if multiple doses/regimens demonstrate a better PK profile or clinical activity) provided that the subject has completed at minimum, the first 28 days of treatment with no sign or evidence of disease progression, no toxicity greater than Grade 2 or the occurrence of significant AEs, and prior approval has been obtained from a GSK medical monitor. Subjects will be permitted to increase dose levels multiple times provided the above criteria are met. Any dose escalations must be agreed upon by the investigator and GSK medical monitor, and must be documented on an Intra-subject Dose Escalation Request Form (see the SPM) with copies maintained at the site and in the study files.

3.6. Rationale

3.6.1. Rationale for Study

HER3 expression is seen across a wide variety of solid malignancies and is associated with poor prognosis. Up-regulation of HER3 expression and activity is also associated

with resistance to multiple pathway inhibitors. GSK2849330, a monoclonal antibody targeting HER3, is a new agent for subjects whose tumors express HER3 and/or its ligand, NRG1. GSK2849330 has a unique pharmacologic profile compared to other HER3 antibodies with multiple modes of action including inhibition of tumor signaling and increased potential for direct cell killing via enhanced ADCC and CDC activities. (See Section 1.2.1 for details).

There is considerable unmet medical need across these tumor types where high HER3 expression is seen. The purpose of the dose escalation is to evaluate safety, PK, and initial PD of the drug in subjects with HER3 expressing tumors. Following dose escalation in Part 1, at least 4 molecularly-defined tumor histology groups will be enrolled in Part 2. Preliminary clinical activity, biomarkers of target engagement, downstream signalling, ADCC, and CDC will be evaluated.

3.6.2. Rationale for Population

Subjects will be selected on the basis of HER3 expression on the cell membrane of the tumor because higher levels of target expression on the cell surface is required for ADCC, CDC and signaling inhibition functions of the antibody. High HER3 expression has been demonstrated in the tumor histologies being considered for this trial [Ocana, 2013].

Study eligibility for Part 1 is based on HER3 protein expression using an analytically validated IHC assay. For some groups in Part 2, study eligibility is further defined by NRG1 expression.

HER3 is expressed in a broad range of solid tumors, including melanoma, gastric cancer, NSCLC, and squamous cell carcinoma of the head and neck (SCCHN). Upon ligand binding, HER3 heterodimerizes with other members of the HER family and acts as a mediator of drug resistance to various cancer therapies [Amin, 2010; Zhang, 2014; Kugel, 2014]. Phosphorylation of intracellular sites of HER3 leads to activation of PI3K/AKT and MEK/MAPK and JAK/STAT signaling. GSK2849330 has demonstrated inhibition of HER3 activity and tumor growth in mouse xenograft models.

For Part 2 of the study, 4 tumor types were selected for inclusion: 2 tumor types with high levels of HER3 expression (melanoma and gastric cancer) and 2 tumor types with high levels of NRG1 (ligand for HER3) expression (cancers of the head and neck and NSCLC).

Melanoma

In melanoma, overexpression of HER3 is associated with advanced disease and decreased survival [Reschke, 2008; Ueno, 2008]. Treatment of melanoma is underexplored in the development of HER3 inhibitors.

In CHL-1, BRAF wild-type melanoma cell line mouse xenograft model GSK2849330 treatment decreased phospho-HER3, total HER3, phospho-AKT and tumor growth.

HER3 inhibition restored the sensitivity of trametinib and dabrafenib (MEK and BRAF inhibitors, respectively) in NRG1-treated BRAF mutant melanoma cell lines.

Gastric cancer

Both HER2 and HER3 expression are probable prognostic markers in patients with gastric cancer [Park, 2006; García, 2003; Piontek, 1993; Hayashi, 2008; Zhang, 2009; Wu, 2014; Sato, 2013].

Approximately 30% to 60% of gastric cancers express HER3 [Hayashi, 2008]. HER3 mutations are present in approximately 11% of gastric cancers. In a gastric cancer xenograft model, HER3 antibodies reported to reduce tumor growths. In NCI-N87, an ERBB2 amplified gastric cancer cell line, GSK2849330 treatment restored sensitivity to lapatinib lost due to the addition of NRG1.

Cancers of the Head and Neck

A subset of head and neck cancer cell lines with sensitivity to lapatinib has elevated expression of NRG1 and activation of HER3 [Wilson, 2011]. High NRG1 expression in these cancers is associated with activation of HER3 and may be used as a predictive biomarker for HER3-targeted therapies [Shames, 2013].

A combination of EGFR and HER3 inhibition caused tumor regression in head and neck xenograft models [Zhang, 2014].

NSCLC

NRG1 overexpression was identified as a biomarker for efficacy in patients treated with HER-3 antibody MM-121 [Sequist, 2014]. In a phase 2 trial of patritumab, a HER3-targeted antibody, in combination with erlotinib, an EGFR inhibitor, in erlotinib-naïve patients with advanced NSCLC, PFS was significantly improved only in the subgroup of patients with high NRG1 expression [Mendell-Harary, 2014; Von Pawel, 2014]. Furthermore, one PR was confirmed in a patient with NSCLC who expressed high levels of NRG1 in a phase 1 study of HER3 antibody AV-203 that included subjects with advanced or metastatic colorectal cancer, NSCLC, and SCCHN, and other solid tumors [Sarantopoulos, 2014]. Recently, NRG1 gene fusion has been reported in a subset of invasive mucinous lung adenocarcinoma.

Nonclinical data also demonstrated NRG1 induced activation of HER3 signalling adversely affect the activity of agents that target the MEK/MAPK and PI3K/AKT signalling pathways. In KRAS mutant NSCLC cell lines, the combined inhibition of MEK and HER3 synergistically induced cell death. HER3 is upregulated in response to AKT inhibition in some NSCLC cell lines. In vitro studies of patritumab showed that only cell lines expressing NRG1 responded to treatment, as manifested by decreases in HER3 and AKT phosphorylation [Schneider, 2014].

